12.5.2.1 Primary Efficacy Analysis

The primary analysis on the primary estimand (see [Section 9.1](#)), the change from baseline to D21 of each treatment period (as defined in [Section 10.2](#) and [Section 10.3](#)) in LLMT-6 (as defined in [Section 10.16](#)) will be analyzed using a linear mixed-effects (LME) model for crossover data (as detailed in [Section 12.5.2.1.8](#)) performed following a multiple imputation strategy applied to missing data (as presented in [Section 12.5.2.1.6](#) and summarized in [Table 12.5-1](#)) during the 51-day randomized efficacy period using FAS.

12.5.2.1.1 Missing Data Handling

As stated in [Section 9.1](#), under the hypothetical strategy for handling intercurrent events, Period 2 data will not be collected when patients discontinue IMP during Period 1. In addition, missing data within a single period only may arise if patients decide to withdraw from the study or are lost to follow-up.

For patients who discontinue study before entering Period 2,

- Not collected Period 1 data will be imputed under the missing at random (MAR) assumption if the patient withdraws from the study due to a reason relative to COVID-19 or if the patient is randomized to the placebo/nabiximols treatment sequence and will be imputed under the control-based missing not at random (MNAR) assumption otherwise (i.e., patient lost to follow up or prematurely withdraws from the study and randomized to nabiximols/placebo treatment sequence),
- Not collected Period 2 data will be imputed under the MAR assumption whether or not missing data arise under the hypothetical strategy and whatever the treatment sequence the patient is randomized to.

For patients who discontinue study but enter in Period 2 not collected Period 2 data will be imputed,

- under the MAR assumption if the patient withdraws from study due to a reason relative to COVID-19 and/or is randomized to the placebo/nabiximols treatment sequence,
- under the control-based MNAR assumption otherwise.

Under this framework, for those patients having their missing scores assumed MNAR, their mean profile will be assumed to be the same as those patients in the placebo treatment arm for the period containing the missing data. Details regarding missing data handling are given in [Table 12.5-1](#) below.

Table 12.5-1 Scenarios for Methods of Imputation when Data are not Collected

Scenario	Missing Data	Period 1 Imputation	Period 2 Imputation
1. Data not collected under the hypothetical strategy for handling intercurrent events	Period 2 data not collected due to patients who discontinue IMP or withdraw during Period 1/washout	N/A	Within treatment arm under MAR
2. Missing data arising due to reasons related to COVID-19, (and/or for patients assigned to placebo/nabiximols treatment sequence assignment)	Period 1 post baseline missing data but patient continues in study at least up to Period 2 baseline	Within treatment arm under MAR	Within treatment arm under MAR
	Period 1 withdrawal	Within treatment arm under MAR	Within treatment arm under MAR (Scenario 1)
	Period 2 post-baseline missing data/withdrawal	N/A	Within treatment arm under MAR

3. Missing data arising due to reasons not related to COVID-19, and not from the placebo/nabiximols treatment sequence assignment	Period 1 post-baseline missing data but patient continues in study	Control-based imputation under MNAR	Control-based imputation under MNAR
	Period 1 withdrawal	Control-based imputation under MNAR	Within treatment arm under MAR (Scenario 1)
	Period 2 post-baseline missing data/withdrawal	N/A	Control-based imputation under MNAR

These scenarios will be applied to the monotone datasets as described in [Section 12.5.2.1.6](#).

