12.5.2.1.6 Pattern Mixture Model Placebo-based Multiple Imputation Method

The Pattern mixture placebo-based multiple imputation method which is a “copy to reference method” will be implemented using baseline to predict D1H3 and D21 values in a MNAR model with indicator variables for treatment period, treatment sequence, and treatment.

For each of the 300 monotone by treatment period datasets generated as described in [Section 12.5.2.1.5](#), the remaining missing data will be imputed separately for each treatment period within each treatment arm using the REGRESSION method in conjunction with the MONOTONE statement and either MNAR or MAR statement (as described in [Table 12.5-1](#)) of the SAS® MI procedure.

- Step1, the imputation model will create 300 monotone by treatment period datasets, as described in [Section 12.5.2.1.5](#).
- Step 2a applied to Period 1 scores,
 - For patients on placebo treatment arm (i.e. placebo/nabiximols treatment sequence) and/or due to COVID-19 with non-missing LLMT-6 baseline score, LLMT-6 scores will be imputed sequentially at each post period baseline assessment (D1H3, D21) using a MAR imputation based on all non-missing LLMT-6 scores. Therefore, the models used to generate each post period baseline LLMT-6 scores are:
 - placebo LLMT-6 Period 1 D1H3 = placebo LLMT-6 Period 1 baseline score.
 - placebo LLMT-6 Period 1 D21 = placebo LLMT-6 Period 1 baseline score and placebo Period 1 D1H3 LLMT-6 score.
 - For patients on nabiximols treatment arm (i.e. nabiximols/placebo treatment sequence) with non-missing LLMT-6 baseline score, LLMT-6 scores will be imputed sequentially at each post period baseline assessment (D1H3, D21) using a MNAR imputation based on all non-missing LLMT-6 scores. Therefore, the models used to generate each post period baseline LLMT-6 scores are:

- nabiximols LLMT-6 Period 1 D1H3 = placebo LLMT-6 Period 1 baseline score.
- nabiximols LLMT-6 Period 1 D21 = placebo LLMT-6 Period 1 baseline score and placebo Period 1 D1H3 LLMT-6 score.
- Step 2b applied to Period 2 scores,
 - For patients on nabiximols treatment arm (i.e. placebo/nabiximols treatment sequence) and/or due to COVID-19 with non-missing LLMT-6 baseline score, LLMT-6 scores will be imputed sequentially at each post period baseline assessment (D1H3, D21) using a MAR imputation based on all non-missing LLMT-6 scores. Therefore, the models used to generate each post period baseline LLMT-6 scores are:

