 - For patients on placebo treatment arm (i.e. nabiximols/placebo treatment sequence) with non-missing LLMT-6 baseline score, LLMT-6 scores will be imputed sequentially at each post period baseline assessment (D1H3, D21) based on all non-missing LLMT-6 scores.
 - If data is missing due to Period 1 withdrawal the procedure will use a MAR imputation and the models used to generate each post period baseline LLMT-6 scores are:
 - placebo LLMT-6 Period 1 D1H3 = placebo LLMT-6 Period 1 baseline score.
 - placebo LLMT-6 Period 1 D21 = placebo LLMT-6 Period 1 baseline score and placebo Period 1 D1H3 LLMT-6 score.
 - If data is missing due to not due to Period 1 withdrawal the procedure will use a MNAR imputation and the models used to generate each post period baseline LLMT-6 scores are:
 - placebo LLMT-6 Period 1 D1H3 = placebo LLMT-6 Period 1 baseline score.
 - placebo LLMT-6 Period 1 D21 = placebo LLMT-6 Period 1 baseline score and placebo Period 1 D1H3 LLMT-6 score.
- Step 3, Each of the 300 LLMT-6 scores generated from the fit of 300 placebo-based imputation models for each missing LLMT-6 score generated in Step 2 will correspond to a unique imputation number, and combination of imputed and non-missing LLMT-6 scores for each result in 300 complete datasets.
- Step 4: Imputed values from each of the 300 imputation datasets selected from step 3 and non-missing LLMT-6 scores will be analyzed by a linear mixed-effects model for crossover data applied to D21 as described in [Section 12.5.2.1.8](#).
- Step 5: Result from each linear mixed-effects model for crossover data will be combined as described in [Section 12.5.2.1.7](#).

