Imputed missing D21 LLMT-6 scores for patients on placebo treatment arm with missing D21 LLMT-6 score as well as for patients on nabiximols treatment arm with either missing D21 LLMT-6 scores due to COVID-19 for those entered in Period 2 or due to study withdrawal during Period 2 will remain MAR (no delta addition) and MI will follow the same approach as the one described in [Section 12.5.2.1.6](#) Step 2b;

The first imputation model (e.g., delta=0) to impute missing D21 LLMT-6 scores for patients on nabiximols treatment arm entered in Period 2 with missing D21 LLMT-6 scores not due to COVID-19 will follow the same MNAR placebo-based MI approach as the one described in [Section 12.5.2.1.6](#) Step 2b.

- Step2c subsequent models

Separately for each treatment period, missing D21 LLMT-6 scores imputed under MAR at Step 2a or Step 2b will remain MAR (no delta addition) whereas for D21 LLMT-6 scores imputed under MNAR at Step 2a or Step 2b, in subsequent models, a common (non-zero) delta value (where delta value represents LLMT-6 score ranging from 0.12 to 5) will be added following MNAR imputation to each imputed value. Delta addition will be obtained using the DELTA option of the MNAR statement of the SAS® MI procedure.

For the first imputation model (delta=0) 300 imputed datasets will be generated at Step 2a and Step 2b. For the subsequent models (delta >0), the same monotone datasets as those used for first imputation model (delta=0) will be retrieved.

- Step 3, the 300 imputation datasets generated from each delta values will be analyzed by a LME model for crossover data applied to D21 as described in [Section 12.5.2.1.8](#).
- Step 4, for each value of delta, results from each LME model for crossover data as described in [Section 12.5.2.1.8](#) will be combined as described in [Section 12.5.2.1.7](#).

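### The primary imputation rule follows treatment sequence, so missing nabiximols scores are placebo-based in Period 1 but MAR in Period 2, and the tipping-point section gives two conflicting rules for Period 2

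*SAP*

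**What the plan says.** SAP Section 12.5.2.1.1 covers patients who entered Period 2 and then left the study. Their missing Period 2 data are imputed as MAR if the withdrawal is due to "COVID-19 and/or is randomized to the placebo/nabiximols treatment sequence", and as control-based MNAR otherwise. In Table 12.5-1 the only MNAR scenario is for data "not related to COVID-19, and not from the placebo/nabiximols treatment sequence assignment". The last row of Scenario 2 puts "Period 2 post-baseline missing data/withdrawal" together under MAR. Scores imputed as MNAR have a mean profile "assumed to be the same as those patients in the placebo treatment arm for the period containing the missing data".

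Section 12.5.2.1.6 repeats the rule. In Step 2a, Period 1 nabiximols scores are placebo-based MNAR. In Step 2b the MAR group is introduced as "For patients on nabiximols treatment arm (i.e. placebo/nabiximols treatment sequence) and/or due to COVID-19 with non-missing LLMT-6 baseline score". The only MNAR branch in Step 2b is for patients then on placebo: "If data is missing due to not due to Period 1 withdrawal the procedure will use a MNAR imputation".

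The tipping-point analysis (Section 12.5.2.2) has two paragraphs for Period 2. The first says that nabiximols scores missing "due to study withdrawal during Period 2 will remain MAR (no delta addition"). The second says that the first imputation model "for patients on nabiximols treatment arm entered in Period 2 with missing D21 LLMT-6 scores not due to COVID-19 will follow the same MNAR" placebo-based approach, citing Step 2b of Section 12.5.2.1.6. Delta is later added to whatever was imputed as MNAR. The section also states that with no penalty the analysis equals the primary analysis.

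**The concern.** Section 12.5.2.1.6 and Appendix 14 describe the primary analysis as placebo-based imputation. The purpose of such a method is to deny the drug effect to patients whose nabiximols data are missing. Because the rule is keyed to sequence, that penalty reaches nabiximols data in Period 1 only.

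The stated hypothetical strategy (Table 9.1-2 and Scenario 1) explains MAR only for Period 2 data never collected after IMP was stopped in Period 1. It does not cover patients who entered Period 2. Patients who stop IMP but stay to the end of the period are observed (Protocol Section 4.1, SAP Table 9.1-2). The affected cases are therefore non-COVID study withdrawals, losses to follow-up and missed D21 visits after entering Period 2 on nabiximols.

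The tipping-point analysis is the planned check on these assumptions. If its text supports two programs, the choice between them could be made after the data are seen.

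**Working it through.** **The rule by cell** (non-COVID, patient entered the period):

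| Missing score | Sequence | Label in the SAP | Profile used |
|---|---|---|---|
| Nabiximols, Period 1 | nabiximols/placebo | MNAR | placebo |
| Nabiximols, Period 2 | placebo/nabiximols | MAR | nabiximols |
| Placebo, Period 1 | placebo/nabiximols | MAR | placebo |
| Placebo, Period 2 | nabiximols/placebo | MNAR | placebo |

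The MNAR label in the last row changes nothing. Step 2b prints the same model lines under its MAR and MNAR placebo branches.

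**The two tipping-point paragraphs.** A non-COVID Period 2 withdrawal on nabiximols meets both. The first paragraph agrees with Table 12.5-1 and with the equality to the primary analysis at delta = 0, but leaves the score unstressed. The second cites a branch that Step 2b does not contain and breaks that equality.

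**Inputs.** SAP Section 8.2 gives an effect of -0.30, an SD of paired differences of 0.71, 46 completers for 80% power, 10% dropout, and 68 completers after re-estimation. A paired t-test reproduces these: power is 0.801 at n = 46; 46/0.9 = 51.1, so 52; power is 0.930 at n = 68 and SD 0.71. Section 8.2 claims at least 80% power at 68 completers under the re-estimated SD, which caps that SD at 0.870.

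Assumptions: 68/0.9 = 75.6, so 76 randomised and 38 per sequence. Let k be the number of affected scores. The documents give no missingness by period, so k is assumed.

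**Primary estimate.** The crossover estimate is the mean of the two within-period contrasts. Moving k Period 2 nabiximols scores to the placebo profile shifts it by at most 0.5 × (k/38) × 0.30. The SE is 0.71/√76 = 0.0814, or 0.870/√76 = 0.0998.

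| k | Shift | In SE, SD 0.71 | In SE, SD 0.87 |
|---|---|---|---|
| 2 | 0.008 | 0.10 | 0.08 |
| 3 | 0.012 | 0.15 | 0.12 |
| 5 | 0.020 | 0.24 | 0.20 |

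These are upper bounds. If, hypothetically, half of the effect were already present at D1H3, simulation gives 0.004, 0.005 and 0.009.

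**Tipping delta, k = 2 in each period, SE fixed, SD 0.71.** The critical estimate is -1.993 × 0.0814 = -0.162.

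- First paragraph: estimate = -0.2921 + 0.0263 × delta, so delta = 4.93.
- Second paragraph: estimate = -0.2842 + 0.0526 × delta, so delta = 2.32.

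At SD 0.87 the values are 3.54 and 1.62. If the variance in each stressed sequence grows by (k/38)(1 - k/38)(0.30 + delta)², they become 3.25 versus 1.74 (SD 0.71) and 2.58 versus 1.31 (SD 0.87). Over k = 2, 3 and 5 per period, the ratio of the two deltas runs from 1.9 to 2.6.

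**Effect of the cap.** Section 12.5.2.1.4 truncates imputed scores at 5, and the delta grid runs from 0 to 5. If truncation is applied after delta and mean LLMT-6 is 2.0, 2.5 or 3.0 (assumed), simulation at k = 2 per period and SD 0.71 found no tipping point in 61%, 85% and 95% of trials under the first paragraph. Under the second, the figures were 0%, 5% and 20%. This used 150 trials per case and 10 imputations, so it is indicative only.

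**The case against.** The sequence rule is stated consistently in Section 12.5.2.1.1, Table 12.5-1 and Steps 2a and 2b, and it can be executed. Protocol Section 13.6.2 specifies only a mixed model, so the SAP adds caution in Period 1 rather than removing any in Period 2. MAR is an ordinary primary assumption, and the shift is at most 0.24 SE. All of this stands. It limits the weight of the primary-analysis point but does not supply the missing rationale.

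The two tipping paragraphs might be reconciled by reading the first as governing withdrawals and the second as governing a D21 visit missed without withdrawal. The SAP does not say so. Table 12.5-1 puts missed data and withdrawal in the same MAR row, so the second paragraph would still contradict the primary rule and the equality at delta = 0. Another sentence in Section 12.5.2.2, that missing nabiximols D21 data are imputed as MNAR, favours the second paragraph, which adds to the ambiguity. The model lines under the Period 2 nabiximols bullet of Step 2b are absent from the text reviewed, possibly an extraction loss, but the bullet itself specifies MAR.

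k is assumed, and 76 - 68 = 8 is the total expected dropout. Two per period uses 4 of the 8; five per period would exceed it. At k = 2 every delta, from 1.3 to 4.9, is at least four times the assumed effect, so a reader might call either result robust. That is fair. The reported tipping point would still differ about two-fold for a reason the plan does not settle.

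The Period 2 placebo reference group has already had nabiximols in Period 1. That is true, but the SAP already names same-period placebo patients as its reference.

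**Conclusion.** The concern holds and should be fixed before unblinding. For patients who entered the period, the primary LLMT-6 and secondary LLMT-4 analyses penalise missing nabiximols data in Period 1 only, without a stated reason. The effect on the estimate is small: at most 0.008 to 0.020 for 2 to 5 affected Period 2 scores, given 38 patients per sequence and a true effect of -0.30.

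The larger fault is in the tipping-point analysis. Its text cannot be programmed without an unspecified choice, and that choice changes the tipping delta by a factor of about two, or may decide whether a tipping point is found at all. The contradiction rests on the text alone. Its numerical size depends on the assumed k, and it disappears if no such Period 2 scores are missing.

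**What to change.** Before unblinding, key the rule in Section 12.5.2.1.1, Table 12.5-1 and Step 2b of Section 12.5.2.1.6 to the treatment in the period (DTRTP) and the COVID flags, all already defined in Section 12.5.2.1.2:

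- Non-COVID missing post-baseline data in a nabiximols period that the patient entered: control-based MNAR from placebo patients of the same period.
- Missing data in a placebo period, COVID-related missing data, and a Period 2 never entered (Scenario 1): MAR.

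Replace the two Period 2 paragraphs of Section 12.5.2.2 with one rule: in both periods, delta is added only to nabiximols D21 scores imputed as MNAR in the primary analysis. Delta = 0 then reproduces the primary analysis. Carry the same wording to LLMT-4 (Section 12.5.3).

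If the sponsor prefers to keep the sequence rule, the SAP should give the reason and still state a single tipping-point rule that agrees with Table 12.5-1.

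The cost is SAP wording and a few lines of SAS, with no new data. Under the treatment-based rule the estimate becomes slightly less favourable to nabiximols if such Period 2 withdrawals occur.

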12.5.2.1.2 Indicator Variables

The following indicator variables will be used to allow inclusion of qualitative variables in the imputation models or to select the imputation strategy as described in [Table 12.5-1](#).

- Treatment arm will be coded as:
 - DTRTP=1 for Nabiximols treatment arm,
 - DTRTP=0 for Placebo treatment arm.
- Treatment sequence will be coded as:
 - DTRTSEQP=1 for Nabiximols/Placebo treatment sequence,
 - DTRTSEQP=0 for Placebo/Nabiximols treatment sequence.
- Impact of COVID-19 on MAS score will be coded as:
 - COVID1=1 if at least score is impacted by the COVID-19 and/or at least one visit impacted by COVID-19 is missed or performed remotely during Period 1 or if the patient withdraws study during Period 1 due to COVID-19;
 - COVID1=0 if no scores are impacted by the COVID-19 and /or no visits are impacted by COVID-19 during Period 1, or if the patient withdraws study during Period 1 not due to COVID-19;
 - COVID2=1 if at least score is impacted by the COVID-19 or at least one visit impacted by COVID-19 is missed or performed remotely during Period 2 or if the patient withdraws study during Period 2 due to COVID-19;
 - COVID2=0 if no scores are impacted by the COVID-19 and /or no visits are impacted by COVID-19 during Period 2, or if the patient withdraws study during Period 2 not due to COVID-19.

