13.1 Sample Size, Power, and Significance Levels

Approximately 26 patients will be randomly assigned to each treatment sequence to ensure that at least 46 patients in total complete the 2 treatment periods. If more than 6 patients withdraw from the trial, additional patients will be enrolled to have 46 completers.

The primary comparison will be the estimate of the mean treatment difference between nabiximols and placebo in the mean change from baseline in Lower Limb Muscle Tone-6 (LLMT-6).

Assuming a standard deviation of the paired differences between nabiximols and placebo of 0.71 and a treatment difference of -0.30, 46 patients will provide 80% power using a 5% significance level and a two-sided test. Adjusting for 10% dropout, a total of approximately N=52 patients is required.

SAS software version 9.4 was used to perform the sample size calculations.

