8.2 Sample Size Considerations

Approximately 26 patients will be randomly assigned to each treatment sequence to ensure that at least 46 patients in total complete the 2 treatment periods. The primary comparison will be the estimate of the mean treatment difference between nabiximols and placebo in the mean change from baseline in LLMT-6.

Assuming a standard deviation of the paired differences between nabiximols and placebo of 0.71 and a treatment difference of -0.30, 46 patients will provide 80% power using a 5% significance level and a two-sided test. Adjusting for 10% dropout, a total of approximately N=52 patients are required. If more than 6 patients withdraw from the trial, additional patients will be enrolled to have 46 completers.

A blinded sample size re-estimation was conducted based on methodology in section 11.1 and the estimated standard deviation of the pooled treatment period differences (treatment period 2 – treatment period 1) in changes from baseline to D21 in MAS was larger than 0.71 (the assumed standard deviation of the treatment differences at design stage). Using this new standard deviation as the estimate of the standard deviation of the treatment differences (nabiximols – placebo) of the changes from baseline to D21 in MAS, the sample size was recalculated. In a blinded sample size re-estimation committee meeting dated 30th November 2021, the committee recommended increasing the sample size to 68 completers. This new sample size will result in at least 80% power for this study if the new observed blinded standard deviation were the true unblinded standard deviation, and greater than 90% power if the true unblinded standard deviation was exactly 0.71.

SAS software version 9.4 was used to perform the sample size calculations.

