12.5.2.2 Sensitivity Analysis – Tipping Point

The primary efficacy analysis assumes data are either missing at random or missing not at random as per missing data handling strategy described in [Section 12.5.2.1.6](#)

To assess the robustness of the treatment effect with regard to missing data, a sensitivity analysis based on a tipping point analysis will be performed for the primary efficacy endpoint to assess the impact of missing data assumed MNAR on the primary estimand.

This analysis will impute missing nabiximols D21 data under a Missing Not at Random assumption, using the FAS, during the 51-day randomized efficacy period (see [Section 10.1](#)).

Thus, when no penalty is added the tipping point analysis is the equivalent to the primary efficacy analysis.

Tipping point analyses

Using monotone datasets generated as described in [Section 12.5.2.1.5](#), the remaining missing data will be imputed separately for each treatment period and each treatment arm using the REGRESSION method in conjunction with the MONOTONE statement and either MNAR statements (for nabiximols treatment arm following imputation strategy described in [Table 12.5-1](#)) or MAR statement (for either placebo treatment arm or nabiximols treatment arm following imputation strategy described in [Table 12.5-1](#)) of the SAS® MI procedure.

- Step1, the imputation model will create 300 monotone datasets, as described in [Section 12.5.2.1.5](#)
- Step 2
 - Step2a for Period 1 - first model

Imputed missing D21 LLMT-6 scores for patients on placebo treatment arm with non-missing baseline score and missing D21 LLMT-6 score as well as for patients on nabiximols treatment arm with non-missing baseline LLMT-6 score and missing D21 LLMT-6 scores due to COVID-19 will remain MAR (no delta addition) and MI will follow the same approach as the one described in [Section 12.5.2.1.6](#) Step 2a

The first imputation model (e.g., delta=0) to impute missing D21 LLMT-6 scores for patients on nabiximols treatment arm with non-missing baseline scores and missing LLMT-6 scores not due to COVID-19 will follow the same MNAR placebo-based MI approach as the one described in [Section 12.5.2.1.6](#) Step 2a.

- Step2b for Period 2 - first model

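### The COVID-19 indicator that can choose between MAR and placebo-based imputation has overlapping codes and no precedence rule, so a Period 1 nabiximols score missing for another reason could be imputed as MAR and spared the tipping-point penalty

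*SAP*

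**What the plan says.** SAP 12.5.2.1.2 introduces indicator variables that enter the imputation models or select the strategy in Table 12.5-1. COVID1 is set to 1 if a score was affected by COVID-19, if "at least one visit impacted by COVID-19 is missed or performed remotely during Period 1", or if the patient withdrew in Period 1 because of COVID-19. It is set to 0 if no scores and/or no visits were affected, "or if the patient withdraws study during Period 1 not due to COVID-19". COVID2 has the same structure for Period 2.

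The rule these flags are meant to serve is worded differently. For a patient who leaves before Period 2, SAP 12.5.2.1.1 imputes Period 1 data as MAR "if the patient withdraws from the study due to a reason relative to COVID-19" or if the patient is in the placebo/nabiximols sequence. Otherwise it uses control-based MNAR. Scenarios 2 and 3 of Table 12.5-1 also turn on why the data are missing.

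The tipping-point section, SAP 12.5.2.2, lets nabiximols patients' "missing D21 LLMT-6 scores due to COVID-19 will remain MAR (no delta addition"). In the later models delta is added only to scores imputed under MNAR. LLMT-4 follows the same scheme (SAP 12.5.3.1 and 12.5.3.2).

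**The concern.** Code 1 looks at what happened at any visit in the period, whereas the rule looks at why the Day 21 score is missing. The two can disagree, and the flag then carries both of its own values.

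What is at stake is the treatment of nabiximols scores lost in Period 1 for reasons unrelated to COVID-19. The plan intends these to borrow the placebo profile and then to carry the delta in the stress test. Under code 1 both protections can go. The choice would fall to whoever programs the flag, in the primary analysis and in the hierarchically tested secondary analysis.

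**Working it through.** **1. The codes applied to one patient.** Sequence nabiximols/placebo; Visit 4 missed because of COVID-19; withdrawal before Visit 5 for an adverse event.

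| Text | Result |
|---|---|
| SAP 12.5.2.1.2, visit limb of code 1 | COVID1 = 1 |
| SAP 12.5.2.1.2, withdrawal limb of code 0 | COVID1 = 0 |
| SAP 12.5.2.1.1 and Table 12.5-1, Scenario 3 | Control-based MNAR |
| SAP 12.5.2.2, if treated as not due to COVID-19 | Delta added |
| Table 12.5-1 and SAP 12.5.2.2, if COVID1 = 1 decides | Within-arm MAR, no delta |

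Protocol 9.1.2.3 schedules MAS at Visit 5 but not Visit 4, so code 1 can apply without any MAS assessment being affected. The and/or in code 0 creates a second overlap: an affected visit with no affected score meets the visit limb of code 1 and the no-score limb of code 0, even without withdrawal.

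**2. The plan's own sample size.** Inputs from SAP 8.2: "standard deviation of the paired differences between nabiximols and placebo of 0.71", "a treatment difference of -0.30, 46 patients will provide 80% power", "using a 5% significance level and a two-sided test". Paired t-test power from the noncentral t with n = 46 is 80.07%, which agrees. The normal approximation gives ((1.960 + 0.842) × 0.71/0.30)² = 43.96. Protocol 13.1 states "Adjusting for 10% dropout, a total of approximately N=52 patients is required"; 46/0.9 = 51.1, rounded up to 52, agrees. After blinded re-estimation the target is 68 completers (SAP 8.2). That gives 93.0% power at SD 0.71, consistent with the SAP's statement of more than 90%, and 80% power up to SD 0.870.

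**3. Shift in the primary difference.** Assumptions not in the documents: 68/0.9 = 75.6, so 76 in the Full Analysis Set and 38 per sequence; true effect -0.30; covariate adjustment and extra imputation variance ignored. The crossover estimate is half the sum of the two within-sequence differences. Moving k Period 1 nabiximols scores between placebo-based and within-arm imputation therefore shifts it by

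k × 0.30/(2 × 38) = 0.0039k.

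This is 0.004 for k = 1 and 0.016 for k = 4. With SE = 0.71/√76 = 0.0814, that is 0.05 to 0.19 SE.

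**4. Plausible k.** At 10% dropout, about 0.10 × 38 = 3.8 nabiximols-first patients leave over both periods, or about 2 in Period 1 if evenly split. A misclassified patient must also have a COVID-affected visit missed or done remotely in the same period. So k = 4 is an outer illustration.

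**5. Tipping point.** Let m be the number of Period 1 nabiximols scores that carry the delta. The estimate is -0.30 + m(0.30 + δ)/76. It loses significance when its size falls to the critical difference c, so

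δ = (0.30 - c) × 76/m - 0.30,

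with c = 0.1623 (SD 0.71) or 0.1989 (SD 0.87). The cap at score 5 is ignored and the SE is held fixed.

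| m | δ, SD 0.71 | δ, SD 0.87 |
|---|---|---|
| 4 | 2.3 | 1.6 |
| 2 | 4.9 | 3.5 |
| 1 | 10.2 | 7.4 |
| 0 | none | none |

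The planned grid runs from 0 to 5. If four leavers are classified correctly, the result tips inside the grid. If all four are coded 1, no Period 1 score carries a delta. Under Step 2b of SAP 12.5.2.1.6 no Period 2 nabiximols score carries one either, so the analysis could not tip.

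**The case against.** The strongest reply is that the rest of the SAP settles the case. Table 12.5-1, SAP 12.5.2.1.1 and the tipping-point text all go by reason, and the last limb of code 0 names the withdrawing patient directly. The flags are not named in SAP 12.5.2.1.6 or 12.5.2.2, and the variable is headed as an effect on MAS scores. This stands as far as it goes: the conservative reading has more support. A reader might infer that non-COVID leavers will get the favourable imputation, and the documents do not support that. They show only that the flag permits it, because SAP 12.5.2.1.2 gives it a selecting role and no precedence.

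A reader might also infer that COVID2 does equal harm. It does not for the primary estimate. Period 2 nabiximols scores belong to the placebo/nabiximols sequence and are MAR whatever COVID2 is (SAP 12.5.2.1.1 and Step 2b). The MAR and MNAR models printed for Period 2 placebo patients are identical. SAP 12.5.2.2 does describe an MNAR model for some Period 2 nabiximols scores. That conflicts with Step 2b and should be aligned.

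Nor is MAR reserved for COVID-19 cases. It also applies to the placebo/nabiximols sequence and to the Period 2 data of everyone who leaves before Period 2.

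Finally, Step 2a prints only placebo models for its MAR group, which includes the COVID-19 cases. Read literally, a nabiximols patient coded 1 would still be imputed from placebo, and only the delta exemption would remain. That disagrees with Table 12.5-1.

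The plan has partial safeguards. Missing patterns are tabulated by COVID-19 impact (SAP 12.5.2.1.3), and completer, on-treatment and COVID-exclusion analyses are planned (SAP 12.5.4.3.2 and 12.5.4.3.4). The COVID-exclusion analysis needs at least 5 patients with affected MAS visits. None of these resolves the code.

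**Conclusion.** Wrong as written, and it should be corrected. The two values of the flag are not mutually exclusive, and code 1 departs from the reason-based rule it is meant to apply. The consequence is essentially confined to Period 1 nabiximols scores.

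On the primary difference it is worth about 0.004 per misclassified patient, under the assumptions of 38 per sequence and a true effect of -0.30. It is nil if Step 2a is taken literally. A material bias in the primary result cannot be inferred: the number of such patients is not in the documents and the planned dropout implies few. The main risk is to the tipping-point analysis, which could look robust only because the scores it should penalise have been exempted.

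**What to change.** - Define COVID1 and COVID2 by the recorded reason that the period's Day 21 LLMT score is missing: 1 only if that reason is COVID-19, 0 otherwise. A non-COVID withdrawal is always 0, even if another visit in the period was affected.
- State that the codes are mutually exclusive and exhaustive, and remove the and/or.
- Use this one flag in SAP 12.5.2.1.1, Table 12.5-1, 12.5.2.1.6 and 12.5.2.2. At the same time align the Step 2a models with the table, and the Period 2 nabiximols text of 12.5.2.2 with Step 2b.
- Assign the flag blinded, before database lock.

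The cost is SAP wording and one derivation rule. New data should not be needed: discontinuation reasons are already summarised (SAP 12.1), and an eCRF form records COVID-19 impact by visit (SAP 12.5.5).

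The downside is that a few more scores may receive the conservative imputation and the delta. Under the assumptions above, power at -0.30 would fall from 95.3% to 94.8% for one such patient and to 93.1% for four (SD 0.71). At SD 0.87 it would fall from 84.3% to 83.3% and 80.2%.
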